CLINICAL STUDY PROTOCOL

Title: A Follow-Up Study to Monitor Therapeutic Response in Transthyretin Cardiac Amyloidosis Using Amyloid Reactive Peptide ¹²⁴I-evuzamitide (AT01) PET/CT

Protocol Version: 2.0

Protocol Date: October 26, 2023

ClinicalTrials.gov: NCT05635045

Sponsor: Columbia University Irving Medical Center
Clinical Cardiovascular Research Laboratory for the
Elderly (CCRLE)
[name]
[name]

Sponsor-Investigator: [name]
[contact]

Collaborating Investigators: [name], PhD
Columbia University Irving Medical Center

[name], DO
Columbia University Irving Medical Center

STUDY SYNOPSIS

Protocol Title	Title: A Follow-Up Study to Monitor Therapeutic Response in Transthyretin Cardiac Amyloidosis Using Amyloid Reactive Peptide ¹²⁴ I-evuzamitide (AT01) PET/CT
Protocol Number	1.0
Design	
This is a single center, prospective cohort study that is evaluating the ability of ¹²⁴I-evuzamitide PET scanning to serially assess and quantify TTR stabilizer and TTR silencer response in the heart in ATTR-CA. 10 subjects will be recruited from our pilot study that have a baseline ¹²⁴I-evuzamitide PET/CT showing cardiac uptake, who are on TTR stabilizer and/or silencer therapy. Data generated from this study will provide amongst the first evidence of changes in myocardial amyloid load on PET/CT imaging with disease modifying therapy and provide preliminary data to support larger investigations in this arena.
 
Consented eligible patients will undergo a single ¹²⁴I-evuzamitide PET scan. Clinically available demographic, clinical and phenotypic data that is collected as part of routine clinical care will be used to characterize the type, severity, and stage of ATTR-CM. Bloodwork, electrocardiograms, and echocardiograms will be performed at the time of the scan.

Study Sites	This study is to be conducted at Columbia University Irving Medical Center.
Time on Study	The duration of patient participation in this study is 31 days.
Primary Objective	To assess and quantify TTR stabilizer and TTR silencer response in the heart in ATTR-CA.
Sample Size	10 patients will be included in this study.
Inclusion and Exclusion Criteria	
10 Participants from the current study on ATTR treatment will be recruited to one cohort.
 
Overall Inclusion Criteria:
 
 1. Must have given written informed consent (signed and dated) and any authorizations required by local law and be able to comply with all study requirements. 2. Were enrolled in the initial pilot using ¹²⁴I-Evuzamitide, on ATTR stabilizer and/or silencer therapy. Able to understand and sign the informed consent document after the nature of the study has been fully explained. 3. TTR genotype shown to be either Val122Ile or wild type. 
The presence of any of the following excludes eligibility for enrollment in this study:

	
 1. Primary amyloidosis (AL) or secondary amyloidosis (AA). 2. Active malignancy or non-amyloid disease with expected survival of less than 1 year. 3. Heart failure, in the opinion of the investigator, primarily caused by something other than amyloidosis. 4. Ventricular assist device. 5. Impairment from stroke, injury or other medical disorder that precludes participation in the study. 6. Disabling dementia or other mental or behavioral disease. 7. Enrollment in a clinical trial not approved for co-enrollment. 8. Continuous intravenous inotropic therapy. 9. Inability or unwillingness to comply with the study requirements. 10. Chronic kidney disease requiring hemodialysis or peritoneal dialysis. 11. Patients taking heparin, or heparin derivatives (e.g. low molecular weight heparins) for anticoagulation. 12. Other reason that would make the subject inappropriate for entry into this study.
Aims	
The specific aim is to determine if ¹²⁴I-evuzamitide PET/CT scanning can:
 
(1) Serially quantify TTR cardiac amyloid load as measured after 1 year of TTR stabilizer and/or silencer treatment.

Safety Assessments	
The safety of study participants will be evaluated by:
 
 1. Assessment of adverse events (AEs), including serious adverse events (SAEs). 2. Vital sign measurements (blood pressure, pulse rate, and respiratory rate). 3. Physical examinations

SCHEDULE OF ACTIVITIES

The following table summarizes the activities to be performed at each of the designated study visits. Details of the different procedures can be found in subsequent sections of this manual.

Procedure	Screening	Historically Obtained Demographic and Clinical Information	¹²⁴ I-evuzamidine PET scanning	Day 7 (+/- 2 days)	Day 28 (+/- 4 days)
Informed Consent	X				
Inclusion and Exclusion Criteria	X				
Medical History		X			
Co-morbidities		X			
ATTR-CM cardiac stage ^a		X			
TTR genotype		X			
Height and Weight [†]			X		
Vitals Signs			X		
Medications		X			
Clinical Examination			X		
Adverse Events Review			X		
KCCQ Questionnaire			X		
Electrocardiogram			X		
Echocardiogram			X		
Bloodwork			X		
^{99m} Tc-PYP Scintigraphy		X			
PET scanning			X		
Follow-Up Safety Call				X	X

^a Stage of ATTR-CM will be defined by criteria as specific in Cheng, R, JACC CardioOncol 2020

Sep;2(3):414-424.

TABLE OF CONTENTS

STUDY SYNOPSIS	2
SCHEDULE OF ACTIVITIES	4
LIST OF ABBREVIATIONS AND DEFINITIONS OF TERMS	7
1. INTRODUCTION	8
1.1 Background and Rationale	8
2. STUDY OBJECTIVES & STUDY DESIGN	11
2.1 Primary Objective	11
2.1.1 Research Goal	11
2.2 Overview of Study Design	12
2.2.1 Methods	12
2.2.2 Study Sites	12
2.2.3 Time on Study	12
2.2.4 Sample Size	12
2.2.5 Patient Recruitment	13
2.2.6 Selection Criteria	13
2.2.7 Cardiac PET/CT with 124I-evuzamitide	13
2.2.8 Statistical Considerations and Sample Size	14
2.2.9 Data Analysis Plan	14
2.3 Limitations and Assumptions	14
3. PATIENT NUMBERING	14
4. ADVERSE AND SERIOUS ADVERSE EVENTS	15
4.1 Adverse Events Definition	15
4.2 Serious Adverse Event (SAE) Definition	15
4.3 Collecting and Reviewing Adverse Event and Outcome Information	15
4.4 Stopping Study Procedure Due to Adverse Event	16
5. ADVERSE EVENT REPORTING	16
5.1 Reporting to the Sponsor	16
5.2 Reporting to the IRB	16
5.3 Reporting to the FDA	17
5.4 Reporting to Participants	17
6. REGULATORY GUIDELINES	18
6.1 Institutional Review Board/Independent Ethics Committee	18
6.2 Regulatory Authorities	18

6.3 Modification of the Protocol	18
6.4 Informed Consent Form	18
6.5 Study Data Handling	19
6.6 Confidentiality	19
REFERENCES	21

LIST OF ABBREVIATIONS AND DEFINITIONS OF TERMS

Abbreviation or Specialist Term	Explanation
99mTc-PYP	99mTechnetium pyrophosphate
AE	Adverse event
SAE	Serios adverse event
TTR	Transthyretin
ATTRv	Variant transthyretin amyloidosis
ATTRwt	Wild-type Transthyretin amyloidosis
ATTR-CA	Transthyretin cardiac amyloidosis
ATTR-CM	Transthyretin amyloid cardiomyopathy
AT-01(¹²⁴ I-evuzamitide)	Pan amyloid imaging peptide labeled with Iodine-124

Several recent studies suggest a promising role of PET imaging in cardiac amyloidosis, and several PET tracers are now available for in vivo detection of amyloid deposits [6-11]. PET imaging has high sensitivity and specificity for amyloid with quantitation and can identify cardiac amyloidosis earlier than Tc99M-PYP scans [11]. PET radiotracers C-11-Pittsburgh compound-B (C-11-PiB), F-18-florbetapir, F-18-florbetaben, F-18-flutemetamol have been approved by the Food and Drug Administration (FDA) for imaging Alzheimer's disease, and have been used successfully in off-label research to image light chain cardiac amyloidosis (AL-CA) and ATTR-CA. Although they are currently not being used in clinical practice, these amyloid PET radiotracers are being investigated for early detection, quantitation, and assessment of response to therapy [6-13]. Multiple studies demonstrated visual uptake of radiotracer and a higher retention index of C-11-PiB in all patients with AL and ATTR compared with control subjects but had the limitation of not distinguishing AL-CA from ATTR-CA; and due to the short half-life of 20 minutes for C-11-PiB, it requires an onsite cyclotron for production [6,14,15]. Further, reports suggested that Tc99M- DPD imaging could be negative despite cardiac amyloid deposition diagnosed by C-11-PiB in certain forms of variant (hereditary) ATTR-CA, such as with the Val30Met variant, where there is a substitution of a single amino acid valine for methionine at position 30 of the TTR gene [15].

A novel amyloid reactive peptide, 124I-evuzamitide, also known as AT01, has been shown to detect various forms of amyloidosis in the liver, spleen, kidney, and bone marrow [16- 18]. We conducted a pilot study at our institution (n=25), where we used 124I-evuzamitide for early detection of ATTR-CA, the assessment of cardiac involvement in rare TTR variants, and the detection and quantification of extra-cardiac amyloidosis [4,19]. PET with molecular imaging could provide detailed information on the extent and quantity of systemic amyloid load, which could be valuable in tracking serially in the context of emerging therapies.

Accordingly, we propose a prospective pilot study using amyloid reactive peptide 124I-evuzamitide PET/CT scans to serially assess and quantify TTR stabilizer and TTR silencer response in the heart in ATTR-CA. 10 subjects will be recruited from our pilot study that have a baseline 124I-evuzamitide PET/CT showing cardiac uptake, who are on TTR stabilizer and/or silencer therapy. Data generated from this study will provide amongst the first evidence of changes in myocardial amyloid load on PET/CT imaging with disease modifying therapy and provide preliminary data to support larger investigations in this arena.

2. STUDY OBJECTIVES & STUDY DESIGN

2.1 Primary Objective

To determine if 124I-evuzamitide PET/CT scanning can quantify and detect changes in myocardial amyloid load with stabilizers and Silencers in ATTR-CA.

2.1.1 Research Goal

The goal of our research is to obtain preliminary data on stabilizer and silencer therapy response to the treatment in ATTR-CA by quantitatively comparing cardiac uptake of 124I- evuzamitide

on PET/CT after one year of disease specific therapy.

The specific aim is to determine if ¹²⁴I-evuzamitide PET/CT scanning can:

- (1) Serially quantify TTR cardiac amyloid load as measured after 1 year of TTR stabilizer and/or silencer treatment.

2.2 Overview of Study Design

We will undertake a prospective cohort study among ATTR-CA subjects that have had ¹²⁴I-evuzamitide PET/CT scan showing cardiac uptake. Eligible subjects, who have already had baseline scans (n=10) will undergo a repeat cardiac PET/CT scan using ¹²⁴I-evuzamitide one year after the baseline scans. Additional information regarding demographic and clinical features including measures of disease severity and stage and TTR genotype will be obtained from previous recent medical encounters. The study will entail a single in-person visit for the whole-body PET scan.

Consented eligible patients will undergo a single ¹²⁴I-evuzamitide PET scan. Cardiac biomarkers and basic metabolic panel, along with quality of life questionnaires, which include: KCCQ, COMPASS 31, SF-36, and EQ-5D-5L and 6-minute walk, will be obtained at the time of the 1-year follow-up scan. Clinically available demographic, clinical and phenotypic data that is collected as part of routine clinical care will be used to characterize the type, severity, and stage of ATTR-CM. An echo will also be obtained at the time of the scan.

2.2.1 Methods

The subjects that will be enrolled will be of variant ATTR-CA (ATTRv) or wild-type ATTR-CA (ATTRwt). Subjects will receive < 1.5 mg of ¹²⁴I-evuzamitide (1 mCi ± 10%), and this will be administered as a single slow IV bolus. PET/CT images will be acquired ~5 hours after dose, as has been demonstrated in our previous studies. 20 minutes of cardiac PET acquisition will be performed.

2.2.2 Study sites

This study is to be conducted at Columbia University Irving Medical Center.

2.2.3 Time on Study

The duration of patient participation in this study is 31 days (for one month follow-up to assess for safety and 3 days of potassium iodide administration prior to PET scanning).

2.2.4 Sample size

10 patients have already been identified who have had baseline scans to be included in this study.

2.2.5 Patient Recruitment

The subjects have been selected from among subjects who underwent 124I-evuzamitide PET/CT scanning previously. All necessary follow-up care or communication of adverse events or incidental findings will either take place as part of the clinical care of the enrolled subjects or be communicated in writing and via telephone with the physician.

2.2.7 Cardiac PET/CT with 124I-evuzamitide

Eligible subjects will begin therapy with potassium iodide (KI) 130 mg orally daily for 3 days prior to receiving 1 mCi 124I-evuzamitide to protect the thyroid. On the day of the scan 124I-evuzamitide will be administered via intravenous push at a proposed rate of ~1 mL per 5 seconds. This dose corresponds to <1.5 mg of AT-01 peptide and 1 mCi +/- 10%). This dosage of 124I-evuzamitide is approximately 38MBq and should be calculated based on the half-life of 96 hours and the date and time of calibration.

Vitals including blood pressure and pulse will be monitored 15 min (+/- 5 minutes) before and after the injection. Cardiac PET/CT images will be acquired at approximately 5 hours post-injection using a low-dose CT (120 kVp, 50 effective mAs). Cardiac PET images will be acquired for 20 minutes. PET data will be reconstructed using a 3DOSEM algorithm with attenuation weighting and prompt gamma correction. PET/CT images will be evaluated for positive radiotracer retention by a nuclear cardiologist blinded to the subjects' history. The retention of 124I-evuzamitide may be quantified from PET/CT images using region-of-interest (ROI) analysis employing a 2D freehand ROI placement method. The data will be expressed as Bq/cc or as standard uptake value ratios (SUVR) using the lumen of the left atrium (blood pool) as the reference tissue.

2.2.8 Statistical Considerations and Sample Size

Given the pilot nature of this investigation, normal formal power calculation was performed.

2.2.9 Data Analysis Plan

Descriptive statistics will be used to summarize subjects' demographics and clinical features. The subjects will be re-randomized for the readers and for quantification. The quantification will be performed using PMOD, and 3 different physicians will be performing quantification individually to verify reproducibility. PET scans will be interpreted by two readers blinded to the clinical information. The organ-specific radioactivity data will be expressed as the mean and standard deviation (SD) of three independent ROIs. The coefficient of variation (COV) will be expressed as (SD/mean)*100.

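### Section 2.2.9 randomizes subjects rather than scans and masks nobody to time point, so knowing which scan is later could bias the one-year change in cardiac uptake

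*Combined protocol and SAP*

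**What the plan says.** The research goal (Section 2.1.1) is a quantitative comparison of cardiac tracer uptake after one year of disease-specific therapy. Section 2.2 has 10 subjects with existing baseline scans returning for one repeat scan a year later; Section 2.2.4 says these 10 are already identified. There is no control group.

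On how the images are read and measured, the plan says:

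- Order of presentation (Section 2.2.9): "The subjects will be re-randomized for the readers and for quantification".
- Quantification (Section 2.2.9): "3 different physicians will be performing quantification individually to verify reproducibility".
- Interpretation (Section 2.2.9): "PET scans will be interpreted by two readers blinded to the clinical information".
- Visual evaluation (Section 2.2.7): images are "evaluated for positive radiotracer retention by a nuclear cardiologist blinded to the" subjects' history.
- Measurement technique (Section 2.2.7): retention may be quantified "using region-of-interest (ROI) analysis employing a 2D freehand ROI placement method".

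The plan does not mention scan date, time point or the order of a subject's two scans when it describes masking or randomization. It does not say whether the baseline scans are measured again with the one-year scans.

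**The concern.** The result that matters is a difference between two measurements on the same person, and each measurement depends on where an operator draws a region by hand. In that setting the most important thing to hide from the operator is which scan came first. History and clinical information are useful to hide, but neither phrase clearly includes scan date, and both are attached to the visual readers rather than to the people who produce the numbers.

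Shuffling subjects changes the order in which patients come up. It does not by itself hide which of a patient's two scans is the later one. If that is visible, a physician's expectation about treatment could affect region placement at one time point and not the other. With no control group, nothing in the design would separate such a shift from a true change. The study is meant to provide some of the first evidence on change under therapy and to support larger studies, so a biased mean change would carry forward into them.

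**Working it through.** **1. Who is masked, and to what.**

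| Role | Section | Masking stated | Time point masked? |
|---|---|---|---|
| Three quantifying physicians | 2.2.9 | None | Not stated |
| Two interpreting readers | 2.2.9 | Clinical information | Not stated |
| One nuclear cardiologist | 2.2.7 | Subjects' history (for positive retention) | Not stated |

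The role that produces the quantitative endpoint is the one with no masking stated. The plan does not say whether the three physicians and the two readers are different people. If they overlap, some quantifiers are blinded to clinical information, but still not expressly to time point.

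**2. What the randomization sentence secures.** Read literally, it permutes 10 subjects. A permutation of subjects is compatible with showing each subject's two scans side by side, dated and in chronological order. It is also compatible with shuffling all 10 × 2 = 20 scans together. Only the second arrangement, with dates removed, hides time point, and the text does not choose between them.

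**3. How a time-point-linked shift enters the result.** Let physician *j* add a shift *b_j* to one-year readings only. Averaged over three physicians and 10 subjects:

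expected mean change = true mean change + (b₁ + b₂ + b₃)/3

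- All three shift by *b*: the bias is *b*, in full.
- One shifts by *b*: the bias is *b*/3. For 5%, 5/3 = 1.7%.

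Averaging over more subjects does not reduce the bias. Averaging over physicians reduces it only where their shifts differ.

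**4. Illustration of scale.** There is no figure in the plan to reproduce: Sections 2.2.8 and 2.2.9 give no SD of change, effect size, test or interval. I assume an SD of percentage change of 10%, 15% or 20%, and use a 95% confidence half-width only as a yardstick:

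half-width = t(0.975, 9 df) × SD/√10 = 2.262 × SD/√10

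| | SD 10% | SD 15% | SD 20% |
|---|---|---|---|
| Half-width | 7.2% | 10.7% | 14.3% |
| Shared shift 2%, as share of half-width | 28% | 19% | 14% |
| Shared shift 5% | 70% | 47% | 35% |
| Shared shift 10% | 140% | 93% | 70% |
| One physician of three shifts 5% (mean moves 1.7%) | 23% | 16% | 12% |

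All SDs and shifts in this table are assumptions. It shows what a shift would do if there were one, and says nothing about how likely one is.

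**5. What masking changes.** If the physicians cannot tell which scan is later, a shift that depends on that knowledge cannot attach to one time point. If both scans are measured in the same procedure, a shift between separate measurement sessions cannot attach to one time point either.

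**The case against.** The best reply is that the sentence already means what it should. This is a single cohort with one new scan each, so there is no treatment to randomize. Randomizing for the readers and for quantification has little evident purpose other than presentation order, and quantification is expressly included. On that reading the gap is one of wording: scans instead of subjects. This is plausible and I cannot exclude it. It still leaves time point unmentioned and the quantifiers' masking unstated.

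Two stronger inferences are tempting, and the documents do not support them. First, a reader might infer that pilot baseline values will be carried forward and that software or region conventions have drifted since. Nothing says so; the inference rests on silence, and randomizing for quantification fits fresh measurement at least as well. Second, a reader might infer that the physicians will share a bias in favour of treatment. Section 2.2.9 has them working individually, and Section 1.1 says it is unclear which way amyloid load moves under therapy. Neither rules out a common shift, but both weaken the case for assuming one, and the one-physician case is much smaller.

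It is also fair that the interval used as a yardstick is not part of the plan, which is descriptive, and that no confirmatory decision rests on a 10-subject pilot. That limits the stakes. A descriptive mean change would, however, be biased by the same amount.

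**Conclusion.** The point holds as a gap in what the text secures, not as a demonstrated bias. Followed literally, Section 2.2.9 allows quantifiers with no stated masking to know which scan is later, in an uncontrolled comparison that depends on freehand regions. The size and direction of any resulting bias cannot be derived from the documents. In the illustration a shared 5% shift ranges from about a third to about two thirds of a confidence half-width, and a one-physician shift of the same size from about an eighth to a quarter; both depend wholly on assumed SDs and shifts. The conclusion assumes that the quantifiers are not all covered by the readers' blinding and that the subject-level wording is not shorthand for pooled, date-stripped scans. If it is shorthand, the change below merely records the intention. I class it as a cheap improvement worth making before quantification starts, with medium confidence.

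**What to change.** Amend Section 2.2.9 to read:

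> All 20 scans (10 baseline, 10 one-year) will be de-identified, stripped of date and time point, and presented in random order. Each of the three physicians will quantify all 20 in one PMOD procedure, masked to time point, and these readings, not earlier pilot readings, will supply the baseline values.

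The same stripped and shuffled set can serve the two interpreting readers.

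**Cost.** At most 10 baseline scans × 3 physicians = 30 re-quantifications of stored images, and none extra if re-measurement is already intended. Section 2.2.9 reports "The organ-specific radioactivity data will be expressed as the mean and standard deviation (SD) of three independent ROIs" without saying whether that means one region per physician or three; if three each, the 30 re-quantifications involve 90 regions. No new scans, patients or readers are needed.

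**Downside.** Random scan order gives up some of the matching of region placement between a subject's two scans.

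**Limit.** The change does not remove acquisition or reconstruction differences between the baseline and one-year scans.

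### The analysis plan summarises spread within a scan but specifies no paired one-year change or interval, and it leaves the uptake measure and the quantifying physicians open

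*Combined protocol and SAP*

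**What the plan says.** Three sections make within-patient change the question. Section 2.1 asks whether PET/CT "scanning can quantify and detect changes in myocardial amyloid load with stabilizers and Silencers in ATTR-CA". Section 2.1.1 proposes to obtain preliminary data "by quantitatively comparing cardiac uptake of" the tracer after one year of therapy. Section 2.2 supplies the pairing: eligible subjects "who have already had baseline scans (n=10) will undergo a repeat cardiac PET/CT scan" one year later. Section 2.2.4 fixes the number: "10 patients have already been identified who have had baseline scans to be included in this study".

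Section 2.2.9 then gives the analysis. Apart from descriptive statistics for demographics and clinical features, its only summaries are "The organ-specific radioactivity data will be expressed as the mean and standard deviation (SD) of three independent ROIs" and a coefficient of variation, SD over mean. Three physicians quantify individually to verify reproducibility, two readers blinded to clinical information interpret the scans, and "The subjects will be re-randomized for the readers and for quantification".

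Section 2.2.7 words quantification as optional and leaves the unit open: "The data will be expressed as Bq/cc or as standard uptake value ratios (SUVR", the latter with left atrial blood pool as reference). The activity given also has a tolerance: "This dose corresponds to <1.5 mg of AT-01 peptide and 1 mCi +/- 10" per cent.

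**The concern.** Followed to the letter, section 2.2.9 produces a mean, an SD and a coefficient of variation for each scan. None of these is a change from baseline, and none says how precisely a change is known. The change statistic and the unit would then be settled after the images have been quantified, in at most 10 pairs, where that choice can alter the message.

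Two further gaps bear on the comparison itself.

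- **Unit.** Bq/cc that is not divided by injected activity scales with the activity given. In SUVR the injected activity cancels.
- **Physicians.** A physician who consistently draws regions high or low adds a constant offset. It cancels in the paired change only if the same physicians quantify both scans. The plan does not say that they do, that baseline images are re-quantified, or that the quantifying physicians are masked to time point. Nor does it say whether the three ROIs are one per physician or several by each, so it is unclear which variability the coefficient of variation measures.

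**Working it through.** The plan states no power, alpha, effect size or SD of change, so it has no figure to reproduce. The checks below size each gap. Inputs from the protocol are n = 10 pairs (2.2.4), three physicians (2.2.9) and activity within 10% of 1 mCi (2.2.7). Section 4.4 allows a scan to be marked incomplete, so 9 and 8 pairs are shown too. All log-scale SDs are assumptions.

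**1. Precision of a paired mean change.** Half-width = t(0.975, n−1) × SD / √n. The last column is exp(half-width × SD), the factor within which the geometric mean ratio would be known.

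| Pairs | Half-width, in SD of change | Factor at log-SD 0.10 / 0.20 / 0.30 |
|---|---|---|
| 10 | 0.715 | 1.07 / 1.15 / 1.24 |
| 9 | 0.769 | 1.08 / 1.17 / 1.26 |
| 8 | 0.836 | 1.09 / 1.18 / 1.29 |

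The planned SD and coefficient of variation do not estimate the SD of change, so they cannot supply this interval.

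**2. Bq/cc and injected activity, with no change in amyloid.**

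- One patient, follow-up tolerance alone: 0.90 to 1.10.
- One patient, opposite extremes at the two scans, if the baseline scan had the same tolerance (assumed): 0.9/1.1 = 0.82 to 1.1/0.9 = 1.22.
- Mean of 10 patients, activity uniform within the tolerance (assumed): the SD of log activity is about 0.058, so the SD of the mean is 0.058/√10 = 0.018. The 95% range of the geometric mean ratio is about 0.96 to 1.03 from follow-up alone. With both scans the SD is multiplied by √2 and the range is about 0.95 to 1.05.

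**3. Physician offsets.** Take offset log-SD τ and SD of change 0.20, so the standard error with 10 pairs is 0.20/√10 = 0.0632. If a shift with SD s is common to all patients, the nominal 95% interval covers with probability P(|t₉| < 2.262/r), where r = √(1 + s²/0.0632²).

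| Arrangement | s | Coverage at τ = 0.05 / 0.10 / 0.15 |
|---|---|---|
| One set of three reads all baseline scans, a wholly different set all follow-up scans | τ√(2/3) | 91% / 80% / 67% |
| One of the three replaced between time points | τ√2/3 | 94% / 90% / 83% |
| Physicians vary patient by patient | no common shift | 95% / 95% / 95% |

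For the first row at τ = 0.10: s = 0.0816, r = 1.633, 2.262/1.633 = 1.385, coverage 80%. In the last row the offsets differ between patients. They widen the SD of change (to √(0.20² + 2τ²/3) = 0.216 at τ = 0.10), and the interval reflects them.

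**4. Reading error.** An SD from three values on one scan has 2 df, with 95% limits of 0.52 to 6.28 times the estimate. Pooled over 20 scans with one value per physician, after removing scan and physician means, it has 60 − 20 − 2 = 38 df and limits of 0.82 to 1.29. With 9 or 8 pairs it has 34 or 30 df.

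**The case against.** The strongest reply is that this is a 10-patient pilot with no planned hypothesis test. Sections 2.1.1 and 2.2 already name a comparison and fix its timing, so anyone can set the two per-scan means side by side. That is fair as far as it goes. The defect is an unspecified summary of a comparison the protocol clearly intends, and the data remain usable. A paired-t interval is also not the only acceptable choice: individual changes with a median and range would be reasonable at this size. But a pilot meant to inform larger studies needs the change and its spread, and section 2.2.9 produces neither.

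Two stronger inferences are tempting, and the documents do not support them.

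- *That different physicians read the two scans, so an interval would be badly wrong.* The protocol describes no such arrangement. Three physicians working individually on re-randomised subjects suggests, if anything, one panel re-reading the images. The 67% to 91% coverage is a worst case requiring complete replacement between time points.
- *That Bq/cc would distort the result by about 20%.* That is a single-patient extreme and assumes the baseline tolerance. Independent deviations largely average out over 10 patients, and what remains would enter a paired interval as added spread.

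The fair statement on both is that the plan leaves the matter open.

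**Conclusion.** The point holds and should be fixed. The objective is a within-patient one-year change, while the stated uptake statistics describe only a single scan. The omission itself is read from the text and rests on no assumed number.

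The effect of the open unit is modest for the group mean and larger for an individual patient's value. The effect of the unstated reading arrangement ranges from nothing (same physicians at both scans, or physicians varying by patient) to serious (complete replacement), depending on facts the protocol does not give. Both sizes rest on the assumptions shown in the working.

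The copy reviewed lacks the text of section 2.2.6. The contents list gives it as selection criteria, so it is unlikely to hold the missing analysis.

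**What to change.** Amend sections 2.2.7 and 2.2.9 as follows.

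1. Make quantification mandatory and name one primary measure that does not depend on injected activity, for example cardiac SUVR with left atrial blood pool as reference. Note that the denominator is itself measured with error. Keep Bq/cc as supporting only.
2. State that the same three physicians quantify the baseline and one-year scans of every patient in one re-randomised order, masked to time point and clinical information, with one value per physician per scan. The existing text blinds the interpreting readers, not explicitly the quantifying physicians, so the masking has to be written in.
3. Primary analysis: each patient's log ratio of one-year to baseline uptake, averaged over physicians; the mean with a paired-t 95% interval on n−1 df, where n is the number of evaluable pairs; and a plot of individual patients by therapy. Describe the estimate as change over one year in patients already on treatment for varying durations, as section 2.3 acknowledges.
4. Report reading error pooled over all scans beside the per-scan coefficient of variation.

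The cost is an amendment with IRB approval (section 6.3), a few hours of analysis, and up to 10 × 3 = 30 re-quantifications of existing baseline images if the re-randomised reading does not already include them. No new scan is needed. The sponsor must accept an interval that will be visibly wide.
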